5.1.1 Risks Associated with RO6867461

5.1.1.1 Important Identified Risks

To date, no identified risks for RO6867461 have been observed.

5.1.1.2 Potential Important Systemic Risks for anti-VEGF Agents

Results from nonclinical studies did not reveal any adverse effects that require specific warnings and precautions that are different from those applicable to any anti-VEGF agents currently used in clinical practice for the treatment of nAMD. Based on previous experience with ranibizumab, important potential risks of RO6867461 include ATEs and immunogenicity to RO6867461.

5.1.1.3 Injection Procedure-Related Risks

IVT injections have been associated with serious adverse reactions related to the injection procedure, including endophthalmitis, rhegmatogenous retinal detachments, and iatrogenic traumatic cataracts. Serious adverse reactions related to the injection procedure have occurred in $<0.1\%$ of IVT injections of ranibizumab ([Lucentis® U.S. Package Insert](#)).

Proper aseptic injection technique should always be used when administering RO6867461. In addition, patients should be monitored following the injection to permit early treatment should an infection occur.

5.1.1.4 Risk of Increased Intraocular Pressure

Increases in IOP have been noted while being treated with repeated IVT injections of anti-VEGF agents, both immediately post-injection (within 60 minutes), as well as pre-injection IOP increases during the duration of studies with monthly treatment administration. Monitoring of IOP prior to and following IVT injection with RO6867461 will be implemented in the Phase II studies. Appropriate management of IOP increases should be initiated as necessary.

5.1.2 Management of Patients Who Experience Specific Adverse Events

Guidelines for management of specific adverse events are outlined in [Table 2](#).

Table 2 Guidelines for Management of Patients Who Experience Specific Adverse Events

Event	Action to Be Taken
Endophthalmitis or severe ocular inflammation (endophthalmitis, 4+ anterior chamber cell/flare or 4+ vitritis; see Section 5.3.5 and Appendix 2 for intraocular inflammation grading scales)	
• Discontinue study treatment.

5.2 SAFETY PARAMETERS AND DEFINITIONS

Safety assessments will consist of monitoring and recording adverse events, including serious adverse events (systemic and ocular) and adverse events of special interest; measurement of protocol-specified safety laboratory assessments; measurement of protocol-specified vital signs; and other protocol-specified tests that are deemed critical to the safety evaluation of the study (i.e., regular ophthalmological monitoring and SD-OCT assessments).

Certain types of events require immediate reporting to the Sponsor, as outlined in Section [5.4](#).

5.2.1 Adverse Events

According to the ICH guideline for Good Clinical Practice, an adverse event is any untoward medical occurrence in a clinical investigation subject administered a pharmaceutical product, regardless of causal attribution. An adverse event can therefore be any of the following:

- Any unfavorable and unintended sign (including an abnormal laboratory finding), symptom, or disease temporally associated with the use of a medicinal product, whether or not considered related to the medicinal product
- Any new disease or exacerbation of an existing disease (a worsening in the character, frequency, or severity of a known condition), except as described in Section [5.3.5.9](#)
- Recurrence of an intermittent medical condition (e.g., headache) not present at baseline
- Any deterioration in a laboratory value or other clinical test (e.g., ECG, X-ray) that is associated with symptoms or leads to a change in study treatment or concomitant treatment or discontinuation from study drug
- Adverse events that are related to a protocol-mandated intervention, including those that occur prior to assignment of study treatment (e.g., screening invasive procedures such as biopsies)

5.2.2 Serious Adverse Events (Immediately Reportable to the Sponsor)

A serious adverse event is any adverse event that meets any of the following criteria:

- Is fatal (i.e., the adverse event actually causes or leads to death)
- Is life threatening (i.e., the adverse event, in the view of the investigator, places the patient at immediate risk of death)

This does not include any adverse event that had it occurred in a more severe form or was allowed to continue might have caused death.

- Requires or prolongs inpatient hospitalization (see Section [5.3.5.10](#))
- Results in persistent or significant disability/incapacity (i.e., the adverse event results in substantial disruption of the patient's ability to conduct normal life functions)
- Is a congenital anomaly/birth defect in a neonate/infant born to a mother exposed to study drug
- Is a significant medical event in the investigator's judgment (e.g., may jeopardize the patient or may require medical/surgical intervention to prevent one of the outcomes listed above)

The terms "severe" and "serious" are not synonymous. Severity refers to the intensity of an adverse event (e.g., rated as mild, moderate, or severe; see Section [5.3.3](#)); the event

itself may be of relatively minor medical significance (such as severe headache without any further findings).

Severity and seriousness need to be independently assessed for each adverse event recorded on the eCRF.

Serious adverse events are required to be reported by the investigator to the Sponsor immediately (i.e., no more than 24 hours after learning of the event; see Section 5.4.2 for reporting instructions).

5.2.3 Adverse Events of Special Interest (Immediately Reportable to the Sponsor)

Non-serious or serious adverse events of special interest are required to be reported by the investigator to the Sponsor immediately (i.e., no more than 24 hours after learning of the event; see Section 5.4.2 for reporting instructions). Adverse events of special interest for this study include the following:

- Cases of potential drug-induced liver injury that include an elevated ALT or AST in combination with either an elevated bilirubin or clinical jaundice, as defined by Hy's law (see Section 5.3.5.6)
- Suspected transmission of an infectious agent by the study drug, as defined below

Any organism, virus, or infectious particle (e.g., prion protein transmitting transmissible spongiform encephalopathy), pathogenic or non-pathogenic, is considered an infectious agent. A transmission of an infectious agent may be suspected from clinical symptoms or laboratory findings that indicate an infection in a patient exposed to a medicinal product. This term applies only when a contamination of the study drug is suspected.

- Sight-threatening adverse events

An adverse event *is* considered to be sight threatening *and* should be reported by the investigator to the Sponsor immediately (i.e., no more than 24 hours after learning of the event; or reporting instructions) if it meets one or more of the following criteria:

- It causes a decrease of ≥ 30 letters in BCVA (compared with the last assessment of VA prior to the most recent treatment) lasting more than 1 hour
- It requires surgical intervention (i.e., conventional surgery, vitreous tap, or biopsy with IVT injection of anti-infectives, or laser or retinal cryopexy with gas) to prevent permanent loss of sight

- It is associated with severe intraocular inflammation (i.e., 4+ anterior chamber cell/flare or 4+ vitritis; see the definitions of intraocular inflammation in Section 5.3.5 and grading scales for assessment in Appendix 2)
- In the opinion of the investigator, it may require medical intervention to prevent permanent loss of sight

5.3 METHODS AND TIMING FOR CAPTURING AND ASSESSING SAFETY PARAMETERS

The investigator is responsible for ensuring that all adverse events (see Section 5.2.1 for definition) are recorded on the Adverse Event eCRF and reported to the Sponsor in accordance with instructions provided in this section and in Section 5.4, Section 5.5, and Section 5.6.

For each adverse event recorded on the Adverse Event eCRF, the investigator will make an assessment of seriousness (see Section 5.2.2 for seriousness criteria), severity (see Section 5.3.3), and causality (see Section 5.3.4).

5.3.1 Adverse Event Reporting Period

Investigators will seek information on adverse events at each patient contact. All adverse events, whether reported by the patient or noted by study personnel, will be recorded in the patient's medical record and on the Adverse Event eCRF.

After informed consent has been obtained **but prior to initiation of study treatment**, only serious adverse events caused by a protocol-mandated intervention (e.g., invasive procedures such as angiographies, discontinuation of medications) should be reported (see Section 5.4.2 for instructions for reporting serious adverse events).

After initiation of study drug, all adverse events will be reported until 28 days after the last dose of study treatment.

Instructions for reporting adverse events that occur after the adverse event reporting period are provided in Section 5.6.

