3. STUDY DESIGN

3.1 DESCRIPTION OF THE STUDY

3.1.1 Overview of the Study Design

This is a Phase II, multicenter, randomized, active comparator-controlled, subject and outcome-assessor masked, parallel group, 52-week study to investigate the efficacy, safety, and pharmacokinetics of RO6867461 administered at 12- and 16-week intervals in treatment-naive patients with nAMD. Approximately 75 patients will be enrolled and randomized in a 2:2:1 ratio to one of three treatment arms:

- Arm A (Q12W): 6 mg RO6867461 IVT every 4 weeks up to Week 12 (4 injections), followed by 6 mg RO6867461 IVT every 12 weeks up to Week 48 (injections at Weeks 24, 36, and 48; 3 injections)
- Arm B (Q16W): 6 mg RO6867461 IVT every 4 weeks up to Week 12 (4 injections), followed by 6 mg RO6867461 IVT every 16 weeks up to Week 48 (injections at Weeks 28 and 44; 2 injections)

A protocol-defined assessment of disease activity at Week 24 requires Arm B patients with active disease (see criteria below) to switch to a 12-weekly dosing regimen of 6 mg RO6867461 for the remainder of the study, with injections commencing at Week 24 and repeated at Weeks 36 and 48.

- Arm C (comparator arm): 0.5 mg ranibizumab IVT every 4 weeks for 48 weeks (13 injections)

Only one eye will be chosen as the study eye.

The total duration of the study for each patient will be up to 56 weeks, divided as follows:

- Screening: up to 4 weeks prior to or on the same day as randomization
- Randomization: Day 1
- Study Treatment Administration: from Day 1 to Week 48
- Final Visit: Week 52

Patients will undergo a screening examination within 4 weeks of study treatment administration. The screening and Week 1/Day 1 (randomization) visit may occur as a combined visit if all assessments (*with the exception of informed consent*) are completed within 48 hours. *Informed consent must be documented before any study-specific screening procedure is performed, and may be obtained more than 28 days before initiation of study treatment.* Where screening and randomization are combined, assessments listed for both visits only need to be conducted once. During screening (or the combined screening/Day 1 visit), the patient's eligibility will be assessed, including a central review of fundus photography (FP), spectral domain optical coherence tomography (SD-OCT), and fundus fluorescein angiography (FFA) to ensure that CNV secondary to AMD meets the predefined ocular criteria in the study.

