If, in the opinion of the investigator, there is significant nAMD disease activity at Week 24 that requires immediate treatment, but does not meet the above criteria, the Medical Monitor should be contacted. In such cases, following approval by the Sponsor, patients randomized to Arm B will receive 6 mg RO6867461 at Week 24 and stay on repeated 12-weekly treatments at Weeks 36 and 48.

Patients who are withdrawn from the study early but have not withdrawn consent should return for an early termination visit 28 (+7) days following the last study treatment for assessments as well as monitoring of all adverse events.

Patients will return for a final visit at Week 52. After the final visit, adverse events should be followed up as outlined in Section 5.6. Assessments performed in case of an unscheduled visit(s) are at the discretion of the investigator.

[Figure 1](#) presents an overview of the study design. A schedule of activities is provided in [Appendix 1](#).

Figure 1 Study Schema

IVT=intravitreal; Q4W=every 4 weeks; Q12W=every 12 weeks; Q16W=every 16 weeks; W=week.

^a All patients will be assessed for disease activity at Week 24. Patients in Arm B who are assessed with active disease at Week 24 will switch to RO6867461 Q12W dosing regimen for the remainder of the study.

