5.4.2.2 Events That Occur after Study Drug Initiation

After initiation of study drug, serious adverse events and adverse events of special interest will be reported until 28 days after the last dose of study drug. Investigators should record all case details that can be gathered immediately (i.e., within 24 hours after learning of the event) on the Adverse Event eCRF and submit the report via the electronic data capture (EDC) system. A report will be generated and sent to Roche Safety Risk Management by the EDC system.

In the event that the EDC system is unavailable, the Serious Adverse Event/Adverse Event of Special Interest Reporting Form provided to investigators should be completed and submitted to the Sponsor or its designee immediately (i.e., no more than 24 hours after learning of the event), either by faxing or by scanning and emailing the form using the fax number or email address provided to investigators. Once the EDC system is available, all information will need to be entered and submitted via the EDC system.

Instructions for reporting serious adverse events that occur >28 days after the last dose of study treatment are provided in Section 5.6.

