5.6 ADVERSE EVENTS THAT OCCUR AFTER THE ADVERSE EVENT REPORTING PERIOD

The Sponsor should be notified if the investigator becomes aware of any serious adverse event that occurs after the end of the adverse event reporting period (defined as 28 days after the last dose of study treatment), if the event is believed to be related to prior study drug treatment. These events should be reported through use of the Adverse Event eCRF. However, if the EDC system is not available, the investigator should report these events directly to the Sponsor or its designee, either by faxing or by scanning and emailing the Serious Adverse Event/Adverse Event of Special Interest Reporting Form using the fax number or email address provided to investigators.

5.7 EXPEDITED REPORTING TO HEALTH AUTHORITIES, INVESTIGATORS, INSTITUTIONAL REVIEW BOARDS, AND ETHICS COMMITTEES

The Sponsor will promptly evaluate all serious adverse events and adverse events of special interest against cumulative product experience to identify and expeditiously communicate possible new safety findings to investigators, IRBs, ECs, and applicable health authorities based on applicable legislation.

To determine reporting requirements for single adverse event cases, the Sponsor will assess the expectedness of these events using the following reference documents:

- RO6867461 Investigator's Brochure
- Ranibizumab U.S. Prescribing Information

The Sponsor will compare the severity of each event and the cumulative event frequency reported for the study with the severity and frequency reported in the applicable reference document.

Reporting requirements will also be based on the investigator's assessment of causality and seriousness, with allowance for upgrading by the Sponsor as needed.

The IMC will monitor the incidence of these expected events during the study. An aggregate report of any clinically relevant imbalances that do not favor RO6867461 will be submitted to health authorities.

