Appendix 1 Schedule of Activities (cont.)

ADA=anti-drug antibody; ALP=alkaline phosphatase; ALT=alanine aminotransferase; AST=aspartate aminotransferase; BCVA=best corrected visual acuity; FFA=fundus fluorescein angiography; HCT=hematocrit; IOP=intraocular pressure; IVT=intravitreal; MCH=mean corpuscular hemoglobin; MCV=mean corpuscular volume; OCT-A=optical coherence tomography angiography; PK=pharmacokinetic; SD-OCT=spectral domain optical coherence tomography; Wk=week.

Notes: There must be a minimum of 21 days between all study visits occurring from Week 4 through Week 52. Standard of care treatment for nAMD in the fellow eye may be provided by the Sponsor as long as the patient remains in the study (see Section 4.4.3). Standard of care treatment after the early termination visit or final visit will not be supplied by the Sponsor.

- ^a The screening and Week 1/Day 1 (randomization) visit may occur as a combined visit if all assessments (*with the exception of informed consent*) are *completed* within 48 hours. Where screening and randomization are combined, assessments listed for both visits only need to be conducted once.
- ^b Patients who are withdrawn from the study early but have not withdrawn consent should return for an early termination visit 28 (+7) days following the last study treatment.
- ^c Assessments performed in case of an unscheduled visit(s) are at the discretion of the investigator.
- ^d Informed consent must be documented before any study-specific screening procedure is performed, and may be obtained more than 28 days before initiation of study treatment.
- ^e A physical examination should cover head and neck including lymph nodes, and the cardiovascular, dermatological, musculoskeletal, respiratory, gastrointestinal, neurological systems, and others as applicable. Any abnormality identified at baseline should be recorded on the General Medical History and Baseline Conditions eCRF. At subsequent visits (or as clinically indicated), limited, symptom-directed physical examinations should be performed. Changes from baseline abnormalities should be recorded in patient's notes. New or worsened clinically significant abnormalities should be recorded as adverse events on the Adverse Event eCRF.
- ^f Vital signs include measurements of pulse rate and systolic and diastolic blood pressure while the patient is in a seated position, and temperature.
- ^g To be performed prior to other ocular assessments.

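### The protocol gives two ends to adverse event reporting, 28 days after the last treatment and the closing visit, and the closing visit may come later

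*Combined protocol and SAP*

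**What the plan says.** Passages that end reporting at 28 days:

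- Section 5.3.1: "After initiation of study drug, all adverse events will be reported until 28 days after the last dose of study treatment". Footnote u, attached to the adverse event row of Appendix 1, repeats this.
- Section 5.4.2.2 sets the same length but counts from study drug: "serious adverse events and adverse events of special interest will be reported until 28 days after the last dose of study drug".
- Section 5.6 asks that later serious events be notified only "if the event is believed to be related to prior study drug treatment". Section 5.3.5.7 ties deaths to the same reporting period and sends later deaths to Section 5.6.

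Passages that point to the closing visit:

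- Section 3.1.1 asks patients withdrawn early, unless they have withdrawn consent, to attend an "early termination visit 28 (+7) days following the last study treatment for assessments as well as monitoring of all adverse events". Its next paragraph places the move to Section 5.6 after the final visit at Week 52, not at day 28.
- The opening of Section 5.3.1 has the investigator ask about adverse events at each patient contact. It has all of them, whether volunteered or noted by staff, entered on the Adverse Event eCRF.
- Appendix 1 marks the adverse event row at Week 52 and at early termination.

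The timing comes from Section 3.1.1 ("Study Treatment Administration: from Day 1 to Week 48") and Appendix 1, where Week 48 is Day 336 (±7) and Week 52 is Day 364 (±7). A note adds: "There must be a minimum of 21 days between all study visits occurring from Week 4 through Week 52". No maximum spacing is given.

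**The concern.** A site that sees a new non-serious event at a closing visit held on day 33 finds two instructions. One says that the reporting period is over. The other says that this visit exists to monitor all adverse events and that everything noted goes on the eCRF. Two sites could handle the same event differently, and both could cite the protocol.

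Under the 28-day rule, the following need not be reported if they begin after day 28 but by the closing visit:

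- non-serious events;
- non-serious events of special interest, which Section 5.2.3 otherwise wants within 24 hours;
- serious events, including deaths, not believed related to study drug.

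Incidence and severity of ocular and non-ocular adverse events are the safety endpoints. Section 6.6 applies no day-28 filter, so the safety tables would carry whatever each site chose to enter. The arms are small: about 75 patients randomized 2:2:1 is roughly 30, 30 and 15. One patient more or fewer with a given event moves that arm's incidence by 1/30 = 3.3 or 1/15 = 6.7 percentage points.

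**Working it through.** Inputs: reporting period 28 days (Sections 5.3.1, 5.4.2.2 and 5.6, footnote u); Week 44, 48 and 52 on Days 308, 336 and 364, each ±7; minimum spacing 21 days (Appendix 1); early termination at 28 (+7) days (Section 3.1.1, Appendix 1).

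1. **Nominal schedule.** 364 − 336 = 28 days, which equals the reporting period. If both visits are on target, there is no gap.

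2. **Week 48 to Week 52 within the windows.**
   - Maximum: (364 + 7) − (336 − 7) = 371 − 329 = 42 days, which is 14 past the limit.
   - Minimum: (364 − 7) − (336 + 7) = 14 days, raised to 21 by the spacing rule.
   - Permitted range: 21 to 42 days.

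3. **Count of permitted day pairs.** With a gap of 28 + d days there are 15 − |d| pairs.
   - d = −7 to 0: 8 + 9 + … + 15 = 92 pairs, at or under 28 days.
   - d = 1 to 14: 14 + 13 + … + 1 = 105 pairs, over 28 days.
   - Share over 28 days: 105 / (92 + 105) = 105/197 = 53%.
   - Mean overrun among the 105: Σ d(15 − d) / 105 = (15 × 105 − 1015) / 105 = 560/105 = 5.3 days.
   - This counts what the schedule allows. It does not forecast when patients will come.

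4. **Early termination.** The visit falls on days 28 to 35 after the last treatment, so never before the limit and at most 35 − 28 = 7 days after it.

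5. **Week 48 treatment missed, Week 52 attended.** The last treatment is then Week 44. The nominal gap is 364 − 308 = 56 days, 28 past the limit. The maximum is 371 − 301 = 70 days, 42 past it.

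6. **With the period ending at the later of day 28 and the closing visit.** The uncovered interval before that visit falls from at most 14 days (Week 52), 7 days (early termination) and 42 days (missed Week 48) to 0 in each case.

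**The case against.** The best defence is that 28 days is a coherent choice: it matches the four-week interval from the last treatment to the final visit, and the gap arises only from window slack or a missed treatment. The 53% is largely what symmetric ±7 windows must produce. A site that follows Section 3.1.1, the opening of Section 5.3.1 and the Appendix 1 row would record late events anyway. Serious events believed related remain notifiable. Laboratory results are summarized separately, and closing-visit images go to the reading center.

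Most of this stands, and it limits the size of the problem. It does not remove the contradiction, because the row that schedules adverse events at the closing visits carries the footnote that ends reporting at day 28.

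A reader might infer three stronger things that the documents do not support:

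- **Anything found at the last examination is lost.** The limit concerns when an event occurs: Section 5.6 and the last paragraph of Section 5.4.2.2 both speak of occurrence. An event that began by day 28 and is found later is inside the period. No rule dates a silent finding to the examination; the nearest, Section 5.3.5.1, dates a diagnosis to its first symptom.
- **Patients who stop early are the most exposed, often having stopped for safety reasons.** Section 4.6.1 also lists withdrawal of consent and non-compliance, and no frequencies are given. Their overrun is at most 7 days, against 14 for patients treated at Week 48.
- **The arms are compared unfairly, or events are certainly under-counted.** Visit windows are the same in all arms, and nothing shows how many events would fall in the interval.

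**Conclusion.** The concern holds as an inconsistency about where the reporting period ends, with a small probable effect. It is not a clear rule that discards closing-visit findings. For most patients the interval in question is a few days of window slack, with permitted maxima of 14 days at Week 52 and 7 at early termination. It is longer, nominally 28 days, only where the Week 48 treatment is missed, and the documents do not say how often to expect that.

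These figures assume that sham counts as study treatment, as Section 4.3.2.1 has it, so that Week 48 is the last treatment in every arm. Section 5.4.2.2 speaks of study drug in one sentence and study treatment in another. If study drug excludes sham, Arm B patients who were not switched have their last dose at Week 44. For them, reporting of serious events and events of special interest would close 28 days after that dose, although Week 52 is nominally 56 days after it. The two terms should be reconciled along with the end date.

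The point is worth correcting because the affected data are the safety endpoints and the change is cheap.

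**What to change.** In Sections 5.3.1, 5.4.2.2 and 5.6 and in Appendix 1 footnote u, define the reporting period as ending 28 days after the last study treatment or at the Week 52 or early termination visit, whichever is later. Use the same term for the starting point in all four places. Apply the same end to deaths (Section 5.3.5.7) and to adverse events of special interest, serious or not. Section 5.6 then applies only after that end, which agrees with Section 3.1.1 and the adverse event row of Appendix 1.

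The cost is one sentence in four places and a consistent reference for deaths and events of special interest. A few more events would be recorded at visits that already take place, so reported incidence may be slightly higher. No visit or procedure is added.
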